12.6 Common Serious Adverse Events

For this protocol, there is no list of common SAEs anticipated for the study population for the purposes of IND safety reporting.

12.7 Clinical Study Continuity

INTRODUCTION

The purpose of this appendix is to provide acceptable alternate methods to assess safety and efficacy parameters, as appropriate, in the event the clinical study is interrupted at the country, state, site or participant level during any crisis (e.g., natural disaster, pandemic).

BENEFIT-RISK RATIONALE

Maintaining the safety of clinical study participants and delivering continuity of care in the clinical study setting is paramount during any crisis. The site is expected to follow the protocol and associated Schedule of Assessments [[Table 1](#)] unless the site principal investigator discusses the need with the Astellas medical monitor to implement the alternate measures.

The approach outlined within this appendix defines which assessments are required to maintain a favorable benefit/risk to the participant, to maintain overall study integrity and to provide acceptable alternate methods to complete the study required assessments and procedures if study activities are unable to be performed as described in [[Section 5 Treatments and Evaluation](#)] due to a crisis.

INFORMED CONSENT

Participants who need to follow any or all of the alternate measures outlined in this Appendix will be required to provide informed consent which explicitly informs them of the nature of, and rationale for these changes, and gain their agreement to continue participation in the study prior to the implementation of any of these changes. In the event the urgency of implementing the alternate measures does not allow for the participant to provide written consent prior to implementation, the principal investigator or designee will obtain oral agreement from the subject followed by written documentation as soon as is feasible. A separate addendum to the study informed consent will be provided to document the participant's consent of the changes.

PARTICIPANT PROCEDURES ASSESSMENT

Sites with participants who are currently enrolled into this clinical study may consider implementing the alternate methods outlined below if one or more of the following conditions are met due to the crisis:

- Regional or local travel has been restricted, inclusive of mandatory shelter in place measures, which makes participant travel to/from the study site nearly impossible
- Site facilities have been closed for clinical study conduct
- Site has been restricted to treating patients with conditions outside of the scope of the study
- Site personnel have temporarily relocated the conduct of the study to a location that place a burden on the participant with respect to time and travel

- Participant(s) have temporarily relocated from the current study site to an alternate study site to avoid placing a burden on the participant with respect to travel
- Participant(s) have temporarily relocated from their home location and the new distances from the site would cause undue burden with respect to time and travel
- Participant has risk factors for which traveling to the site poses an additional risk to the participant's health and safety

Adherence to the original protocol as reflected in the Schedule of Assessment [Table 1] is expected, where plausible, in the case of a crisis. The alternate measures as noted in Table 3 below are only permissible in the event of a crisis, and after discussing the need with the Astellas medical monitor to implement the alternate measures. This is to allow for continuity of receiving investigational medicinal product (IMP) and maintaining critical safety and efficacy assessments for patients participating in the study at a time of crisis.

If one or more of the alternate measures noted below is implemented for a participant, the site should document in the participant's source document the justification for implementing the alternate measure and the actual alternate measures that were implemented, along with the corresponding time point(s).

Table 3 Alternative Schedule of Assessments in Response to a Crisis

Assessments	Alternate Approaches	Treatment Period									Follow-up Visit
		Visit 2b	Visit 3	Visit 4	Visit 5	Visit 6	Visit 7	Visit 8	Visits 9, 10, 11, 12, 13 and 14	Visit 15/ EOT/ED	Visit 16
Study Visit		Week 2	Week 4	Week 8	Week 12	Week 16	Week 20	Week 24	Weeks 28, 32, 36, 40, 44 and 48	Week 52	Week 55
Time of Visit		Day 15	Day 29	Day 57	Day 85	Day 113	Day 141	Day 169	Day 197, 225, 253, 281, 309 and 337	Day 365	Day 386
Visit days		± 3	± 3	± 3	± 3	± 3	± 3	± 3	± 3	-14 /+ 6	± 3
Visit Window (days)											
Mammogram	If imaging is delayed, should be completed as soon as possible.	Please refer to protocol schedule of assessments.									
Demographic data	Remote/Virtual/Telemedicine Visits allowed	Please refer to protocol schedule of assessments.									
Urine pregnancy test	Visit collection of samples at local facility acceptable if results can be made available to investigative site. To be completed at local laboratory.	Please refer to protocol schedule of assessments.									
Clinical laboratory	Visit collection of samples at local facility acceptable if results can be made available to investigative site. To be completed at local laboratory.	Please refer to protocol schedule of assessments.									
Serology	Visit collection of samples at local facility acceptable if results can be made available to investigative site. To be completed at local laboratory.	Please refer to protocol schedule of assessments.									
Blood pharmacodynamic sample	Delay the measurements to subsequent visit.	Please refer to protocol schedule of assessments.									
Blood pharmacokinetic sample	Delay the measurements to subsequent visit.	Please refer to protocol schedule of assessments.									

Table continued on next page

Assessments	Alternate Approaches	Treatment Period									Follow-up Visit
		Visit 2b	Visit 3	Visit 4	Visit 5	Visit 6	Visit 7	Visit 8	Visits 9, 10, 11, 12, 13 and 14	Visit 15/ EOT/ED	
Study Visit											
Time of Visit		Week 2	Week 4	Week 8	Week 12	Week 16	Week 20	Week 24	Weeks 28, 32, 36, 40, 44 and 48	Week 52	Week 55
Visit days		Day 15	Day 29	Day 57	Day 85	Day 113	Day 141	Day 169	Day 197, 225, 253, 281, 309 and 337	Day 365	Day 386
Visit Window (days)		± 3	± 3	± 3	± 3	± 3	± 3	± 3	± 3	-14 /+ 6	± 3
C-SSRS	Remote/Virtual/Telemedicine Visits allowed	Please refer to protocol schedule of assessments.									
EQ-5D-5L	Remote/Virtual/Telemedicine Visits allowed for non-dosing visits	Please refer to protocol schedule of assessments.									
MENQoL	Remote/Virtual/Telemedicine Visits allowed for non-dosing visits	Please refer to protocol schedule of assessments.									
ePRO training	Remote/Virtual/Telemedicine Visits allowed for non-dosing visits	Please refer to protocol schedule of assessments.									
Dispense study drug	Patients can be brought into the clinic earlier to provide additional study drug. Courier service directly to patient allowed.	Please refer to protocol schedule of assessments.									
Study drug compliance and accountability	Patients can be brought into the clinic earlier to provide additional study drug. Courier service directly to patient allowed.	Please refer to protocol schedule of assessments.									
Concomitant medications and AEs	Remote/Virtual/Telemedicine Visits allowed for non-dosing visits	Please refer to protocol schedule of assessments.									

AE: adverse event; C-SSRS: Columbia Suicide Severity Rating Scale; ED: early discontinuation; EOT: end of treatment; ePRO: electronic patient-reported outcome; EQ-5D-5L: Euro-Qol 5D-5L; MENQoL: Menopause-Specific Quality of Life.

INVESTIGATIONAL MEDICINAL PRODUCT SUPPLY

If any of the conditions outlined above in the Participants Procedures Assessment are met, one or all of the following mitigating strategies will be employed, as needed, to ensure continuity of IMP supply to the participants:

- Increase stock of IMP on site to reduce number of shipments required, if site space will allow.
- Direct-to-Participant shipments of IMP from the site to the participant's home.
- Bringing the participant to the site earlier.

DATA COLLECTION REQUIREMENTS

Additional data may be collected in order to indicate how participation in the study may have been affected by a crisis and to accommodate data collection resulting from alternate measures implemented to manage the conduct of the study and participant safety.

- Critical assessments for safety and efficacy based on study endpoints to be identified as missing or altered (performed virtually, at alternative locations, out of window, or other modifications) due to the crisis.

13 ATTACHMENT 1: NONSUBSTANTIAL AMENDMENT 3

I. The purpose of this amendment is:

Nonsubstantial Changes
1. Update End of Treatment (EOT) Visit Window
DESCRIPTION OF CHANGE:
The EOT visit window is expanded from 0/+6 to -14/+6 and a footnote is added to the endometrial biopsy at Visit 15/EOT/early discontinuation.
RATIONALE:
This is to provide more flexibility to investigators and subjects in scheduling the EOT/ED visit, to ensure that there is appropriate opportunity to collect all EOT/ED assessments. In case of an EOT/ED endometrial biopsy that is evaluated as ‘insufficient material’ or ‘unevaluable’, the extended visit window will enable a retest biopsy to be conducted within the visit window.
2. Clarification of Visit 15/EOT/ED Endometrial Biopsy Procedures
DESCRIPTION OF CHANGE:
Language is added to clarify that EOT/ED endometrial biopsies that are evaluated as ‘insufficient material’ or ‘unevaluable’ a retest biopsy is required. In addition, language was also added to clarify when a repeat biopsy is required.
RATIONALE:
This change is made to further optimize the collection of EOT/ED endometrial biopsies for the primary objective/endpoint of the study and provide clarity on when a repeat biopsy is required.
3. Add Clarification for Pharmacokinetic Sample at Week 52
DESCRIPTION OF CHANGE:
A statement added to the footnote for Blood Pharmacokinetic Sample in the schedule of assessments to clarify that the last dose of study drug should be administered the day prior to the week 52 (visit 15) visit.
RATIONALE:
This revision is made for clarification.
4. Update Timing of Week 52 Dual-Energy X-Ray Absorptiometry (DXA)
DESCRIPTION OF CHANGE:
In Section 5.5.2 and the schedule of assessments, the timing of the week 52 DXA is changed to ‘between week 50 and 52.’

RATIONALE:
This revision is made to align with the timing of the adjusted Visit 15/EOT/ED visit window.
5. Clarification of Recording an Abnormal Endometrial Biopsy as an Adverse Event (AE)
DESCRIPTION OF CHANGE:
Added that the investigator should record any abnormal biopsies and the associated diagnostic and therapeutic measures, as an AE.
RATIONALE:
Clarification provided to investigator so abnormal endometrial biopsies can be followed to resolution.
6. Removed Platelet Reduction as AE of Special Interest
DESCRIPTION OF CHANGE:
Platelet reduction is removed as an AE of special interest
RATIONALE:
Not consistent with the statistical analysis plan.
7. Removed Significance Testing
DESCRIPTION OF CHANGE:
Removed the significance testing for dichotomized endpoints.
RATIONALE:
The confidence intervals for odds ratio and rate is sufficient for interpretation.
8. Add Appendix for Clinical Study Continuity
DESCRIPTION OF CHANGE:
A Clinical Study Continuity appendix is added to the protocol (Appendix 12.7). This appendix contains procedures for continuity of care during a crisis (e.g., natural disaster or a pandemic).
RATIONALE:
This appendix is added to provide acceptable alternate methods to assess safety and efficacy parameters in the event the clinical study is interrupted at the country, state, site or participant level during any crisis (e.g., natural disaster or pandemic). This is an appendix that is being standardized throughout Astellas. The procedures that are included in this appendix are aligned with what was already included in the previous version of the protocol.

9. Minor Administrative-type Changes
DESCRIPTION OF CHANGE:
Include minor administrative-type changes (e.g., typos, format, numbering and consistency throughout the protocol) and updated list of abbreviations.
RATIONALE:
To provide clarifications to the protocol and to ensure complete understanding of study procedures.

II. Amendment Summary of Changes:

II Contact Details of Key Sponsor's Personnel
WAS:

PPD [Redacted] ICON Clinical Research
 
PPD [Redacted]

IS AMENDED TO;

PPD [Redacted] ICON Clinical Research
 
PPD [Redacted]

III List of Abbreviations and Definition of Key Terms List of Abbreviations	
ADDED:	
IMP	investigational medicinal product

V Flow Chart and Schedule of Assessments*Table 1 Schedule of Assessments*

WAS:

Assessments	Screening Visit ^{a,x}	Randomization ^x	Treatment Period									Follow-Up Visit ^b
			Visit 2b	Visit 3	Visit 4	Visit 5	Visit 6	Visit 7	Visit 8	Visits 9, 10, 11, 12, 13 and 14	Visit 15/EOT/ED ^x	
Study Visit	Visit 1	Visit 2	Visit 2b	Visit 3	Visit 4	Visit 5	Visit 6	Visit 7	Visit 8	Visits 9, 10, 11, 12, 13 and 14	Visit 15/EOT/ED ^x	Visit 16
Time of Visit	Week -5 to -1	Week 0	Week 2	Week 4	Week 8	Week 12	Week 16	Week 20	Week 24	Weeks 28, 32, 36, 40, 44 and 48	Week 52	Week 55
Visit days	Days -35 to -1	Day 1	Day 15	Day 29	Day 57	Day 85	Day 113	Day 141	Day 169	Day 197, 225, 253, 281, 309 and 337	Day 365	Day 386
Visit Window (days) ^c	-35 to -1	-	± 3	± 3	± 3	± 3	± 3	± 3	± 3	± 3	+ 6	± 3
Endometrial biopsy ⁿ	X										X	
DXA ^o	X										X	
Serology ^p	X											
Blood pharmacodynamic sample ^q		X		X		X			X		X	X
Blood pharmacokinetic sample ^r				X ^r		X			X		X	
C-SSRS ^s	X	X				X			X		X	X
EQ-5D-5L ^t		X		X		X			X		X	
MENQoL ^t		X		X		X			X		X	
Dispense study drug ^u		X		X	X	X	X	X	X	X		
Study drug compliance and accountability ^v		X		X	X	X	X	X	X	X	X	
Concomitant medications and AEs ^w	X	X	X	X	X	X	X	X	X	X	X	X

n. Endometrial biopsy will be performed at screening and at week 52/EOT and in the case of uterine bleeding during treatment. Subject may schedule the endometrial biopsy on a separate day, within the screening period. Subjects that require a retest biopsy due to insufficient or unevaluable result, will have an extended screening period and will be allowed an additional 15 days of screening (i.e., days -50 to -1). Screening biopsy results are valid for study entry up to 3 months from date of procedures for applicable subjects. Subjects who screen failed due to the COVID-19 pandemic study suspension and have a documented evaluable endometrial biopsy from the original screening period do not have to undergo a repeat biopsy should they decide to rescreen. If a subject discontinues from the study, an endometrial biopsy will be performed at the discontinuation visit along with all other EOT procedures.

p. For practical reasons, the timing of DXA may vary from the actual time of the visit, depending on the DXA availability (DXA appointment). The screening visit (days -35 to -1 [visit 1]) DXA can be performed once the subject has been deemed eligible based on screening laboratory tests, or at visit 2 but must be performed before randomization. The week 52 (visit 15) DXA should be performed between week 51 and week 52, inclusive. For subjects who are withdrawn from the study prior to completion, a DXA will be completed as soon as possible after study drug discontinuation

(preferably within 2 weeks).

- s. Pharmacokinetic samples to be taken predose at week 4 (visit 3), week 12 (visit 5), week 24 (visit 8), and at EOT/ED week 52 (visit 15) and at 1 to 3 hour postdose at week 4 (visit 3). A predose sample will be collected for any subject with a signal of elevated ($> 3 \times \text{ULN}$) transaminases.
- v. Subjects will be assigned study drug as a kit containing either fezolinetant or placebo. Study drug intake will be done with a glass of room temperature tap water. The first intake of study drug will take place at the study site on day 1 (visit 2) under the supervision of the study staff. On study visit days, the daily dose of study drug will be taken at the study site, under the supervision of the study staff, after collection of predose blood samples. On all other days throughout the treatment period, subjects will be instructed to take their study drug at home, in the morning with water.

IS AMENDED TO:

Assessments	Screening Visit ^{a,x}	Randomization ^x	Treatment Period									Follow-Up Visit ^b
			Study Visit	Visit 1	Visit 2	Visit 2b	Visit 3	Visit 4	Visit 5	Visit 6	Visit 7	
Time of Visit	Week -5 to -1	Week 0	Week 2	Week 4	Week 8	Week 12	Week 16	Week 20	Week 24	Weeks 28, 32, 36, 40, 44 and 48	Week 52	Week 55
Visit days	Days -35 to -1	Day 1	Day 15	Day 29	Day 57	Day 85	Day 113	Day 141	Day 169	Day 197, 225, 253, 281, 309 and 337	Day 365	Day 386
Visit Window (days) ^c	-35 to -1	-	± 3	± 3	± 3	± 3	± 3	± 3	± 3	± 3	-14/+ 6	± 3
Endometrial biopsy ⁿ	X ⁿ										X ^o	
DXA ^{op}	X										X	
Serology ^{oq}	X											
Blood pharmacodynamic sample ^{or}		X		X		X			X		X	X
Blood pharmacokinetic sample ^{os}				X ^r		X			X		X	
C-SSRS ^{ot}	X	X				X			X		X	X
EQ-5D-5L ^{ou}		X		X		X			X		X	
MENQoL ^{ou}		X		X		X			X		X	
Dispense study drug ^{ov}		X		X	X	X	X	X	X	X	X	
Study drug compliance and accountability ^{ow}		X		X	X	X	X	X	X	X	X	
Concomitant medications and AEs ^{wx}	X	X	X	X	X	X	X	X	X	X	X	X

- v. Endometrial biopsy will be performed at screening and at week 52/EOT and in the case of uterine bleeding during treatment. Subject may schedule the endometrial biopsy on a separate day, within the screening period. Subjects that require a retest biopsy due to insufficient or unevaluable result, will have an extended screening period and will be allowed an additional 15 days of screening (i.e.,

days -50 to -1). Screening biopsy results are valid for study entry up to 3 months from date of procedures for applicable subjects. Subjects who screen failed due to the COVID-19 pandemic study suspension and have a documented evaluable endometrial biopsy from the original screening period do not have to undergo a repeat biopsy should they decide to rescreen. ~~If a subject discontinues from the study, an endometrial biopsy will be performed at the discontinuation visit along with all other EOT procedures.~~

- o. Endometrial biopsy is required at EOT or ED. For EOT/ED week 52 (visit 15) biopsies that are evaluated as insufficient material or unevaluable, a retest biopsy will be required. Any of the three pathologists can determine if a EOT/ED biopsy is insufficient or unevaluable. However, if two pathologists read the EOT/ED endometrial biopsy as evaluable and issue the same diagnosis, and the 3rd pathologist reads the biopsy as insufficient or unevaluable, the biopsy does not need to be repeated.**
- ep** For practical reasons, the timing of DXA may vary from the actual time of the visit, depending on the DXA availability (DXA appointment). The screening visit (days -35 to -1 [visit 1]) DXA can be performed once the subject has been deemed eligible based on screening laboratory tests, or at visit 2 but must be performed before randomization. The week 52 (visit 15) DXA should be performed between week ~~50~~ and week 52, inclusive. For subjects who are withdrawn from the study prior to completion, a DXA will be completed as soon as possible after study drug discontinuation (preferably within 2 weeks).
- rs** Pharmacokinetic samples to be taken predose at week 4 (visit 3), week 12 (visit 5), week 24 (visit 8), and at EOT/ED week 52 (visit 15) and at 1 to 3 hour postdose at week 4 (visit 3). A predose sample will be collected for any subject with a signal of elevated ($> 3 \times \text{ULN}$) transaminases. **For the week 52 (visit 15) PK/PD samples, the last dose of study drug should be administered the day prior to the week 52 (visit 15) visit. Sites should collect week 52 (visit 15) PK/PD samples approximately at the same time when study drug would typically be given on site.**
- v. Subjects will be assigned study drug as a kit containing either fezolinetant or placebo. Study drug intake will be done with a glass of room temperature tap water. The first intake of study drug will take place at the study site on day 1 (visit 2) under the supervision of the study staff. On study visit days (**except for EOT/ED week 52 [visit 15]**), the daily dose of study drug will be taken at the study site, under the supervision of the study staff, after collection of predose blood samples. On all other days throughout the treatment period, subjects will be instructed to take their study drug at home, in the morning with water.

IV Synopsis, Study Design Overview and 2 Study Objectives, Design, and Endpoints

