- a. The screening visit is to occur on or within 35 days of randomization (day 1 [visit 2]). Subjects may be retested 1 time for assessments upon approval of the medical monitor. An extra 15 screening days are allowed for repeat biopsy, if necessary (days -50 to -1, including the screening visit [visit 1] assessments). The following assessments do not need to be repeated at the rescreen provided they still fall within the acceptable screening time window: TVU, DXA, endometrial biopsy, mammogram, ECG and Pap test (or equivalent cervical cytology). Subjects who screened for the 2693-CL-0301 or the 2693-CL-0302 study that did not meet the minimum requirement for frequency and severity of VMS prior to randomization may be re-screened for this study. The following assessments do not need to be repeated at the rescreen provided they still fall within the acceptable screening time window: TVU, endometrial biopsy, mammogram, ECG and Pap test (or equivalent cervical cytology). History of average caffeinated beverage intake will be collected at baseline. At each clinic visit, the caffeinated beverage intake within the past 24 hours will be recorded.
- b. The follow-up visit (visit 16) will occur approximately 3 weeks following the last dose of study drug.
- c. Subjects will return to the study site for visits and procedures to occur within ± 3 days of the scheduled day. Unscheduled visits can be planned outside the scheduled visits.
- d. Signed informed consent will be collected for all subjects before any study-related procedures are conducted.
- e. At screening, in the event that the subject does not have a documented normal/negative or no clinically significant findings mammogram from the previous 12 months on record. A mammogram at week 52/EOT/ED will be conducted if it coincides with the regularly scheduled routine screening mammogram of the patient, in accordance with local medical practice guidelines and the patient's primary care physician.
- f. Includes age, race, sex and smoking status (smoker/non-smoker), etc. Demographic information may vary based on country requirements.
- g. Includes height (at the screening visit only), weight and waist circumference. A bimanual clinical pelvic and clinical breast examination will be performed at the screening visit. A bimanual clinical pelvic examination can be performed at any time in the study where clinically indicated.

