- p. For practical reasons, the timing of DXA may vary from the actual time of the visit, depending on the DXA availability (DXA appointment). The screening visit (days -35 to -1 [visit 1]) DXA can be performed once the subject has been deemed eligible based on screening laboratory tests, or at visit 2 but must be performed before randomization. The week 52 (visit 15) DXA should be performed between week 50 and week 52, inclusive. For subjects who are withdrawn from the study prior to completion, a DXA will be completed as soon as possible after study drug discontinuation (preferably within 2 weeks).
- q. For HBsAG, anti-HCV antibodies, anti-HBs antibodies, anti-HBc antibodies and anti-HIV antibodies.
- r. Pharmacodynamic samples will be taken predose (1 hour) at day 1 (visit 2), week 4 (visit 3), week 12 (visit 5), week 24 (visit 8), at week 52 (visit 15) and week 55 (visit 16). Markers include LH, FSH, E2, SHBG, androstenedione, dehydroepiandrosterone, estrone and testosterone.
- s. Pharmacokinetic samples to be taken predose at week 4 (visit 3), week 12 (visit 5), week 24 (visit 8), and at EOT/ED week 52 (visit 15) and at 1 to 3 hour postdose at week 4 (visit 3). A predose sample will be collected for any subject with a signal of elevated ($> 3 \times$ ULN) transaminases. For the week 52 (visit 15) PK/PD samples, the last dose of study drug should be administered the day prior to the week 52 (visit 15) visit. Sites should collect week 52 (visit 15) PK/PD samples approximately at the same time when study drug would typically be given on site.
- t. A clinician will administer the C-SSRS measure electronically at the clinic visit, prior to any invasive procedures. This will be administered electronically via the site tablet at screening, (visit 1), week 0 (visit 2), week 12 (visit 5), week 24 (visit 8), EOT/ED week 52 (visit 15) and the follow-up visit (week 55 [visit 16]).

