1.3.2 Summary of Clinical Studies

To date, 10 clinical studies have been completed with fezolinetant; 6 phase 1 studies (ESN364-CPK-101, ESN364-CPK-102, ESN364-CPK-103, 2693-CL-0020, 2693-CL-0006 and 2693-CL-009) and 4 phase 2 studies (ESN364-HF-204, ESN364-UF-02, ESN364-PCO-201 and ESN364_HF_205). Two of the 4 phase 2 studies were performed in women with MR-VMS (Studies ESN364_HF_204 and ESN364_HF_205). The 10 completed studies with fezolinetant are shown in [Table 2](#).

The pharmacokinetics of fezolinetant were characterized in studies in healthy subjects and in patients with VMS. After oral intake, fezolinetant showed generally dose proportional pharmacokinetics at doses between 20 and 60 mg once daily in female subjects. Maximum concentration (C_{max}) was generally reached within 1 to 4 hours postdose with terminal half-life ranging between 4-6 hours in healthy subjects and patients. With a once daily dose regimen, steady state plasma concentrations were achieved by approximately day 2 with minimal accumulation. Low plasma protein binding of fezolinetant (50%) was observed with almost equal distribution of fezolinetant into red blood cells and plasma, with a blood-to-plasma ratio of 0.9.

Fezolinetant undergoes extensive metabolism, primarily by cytochrome P450 (CYP) 1A2 enzyme, to form the major metabolite ES259564. A strong CYP1A2 inhibitor (fluvoxamine) increased fezolinetant area under the concentration-time curve (AUC) and C_{max} approximately 9-fold and 1.8-fold, respectively, while smoking was shown to decrease AUC and C_{max} to a geometric least squares mean ratio of 48.3% and 71.7%, respectively (2693-CL-0006).

In a recently completed mass balance study (ESN364_CPK_103), the routes of excretion of fezolinetant were found to be via urine (76.9%) and feces (14.7%). In urine, a mean of 1.1% of the administered fezolinetant dose was excreted unchanged and 61.7% of the administered dose was excreted as metabolite ES259564.

Fezolinetant did not show clinically significant food effects on its pharmacokinetic exposure parameters (ESN364_CPK_101). Based on population pharmacokinetic modeling analyses, body weight was not identified as an important predictor of AUC. However, male subjects are predicted to have 53.2% reduction AUC and 14.9% reduction in C_{max} , compared to females. Asian population was predicted to have a 25% increase in steady-state C_{max} and AUC, which is consistent with clinical observations (Study 2693-CL-0020)

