6.10 Additional Conventions

6.10.1 Analysis Windows

Study Day for analysis windows will be calculated as date of visit/assessment – first dose date +1.

Study Day for the follow-up (FUD) phase will be calculated as date of visit/assessment – last dose date of study treatment (Date of EOT).

Except for adverse events, for the analysis window (weeks prior to the follow-up period), the last day is always 1 day after the last day of exposure to double-blind treatment.

The end of overall treatment is defined as the last day of treatment +1 and the follow-up period begins at last overall treatment + 2 days and onward (Follow-up Study Day 2).

The data summary by visits will be done following the analysis windows specified in the table below:

Analysis	Scheduled	Analysis Windows (day)				
Visits	Day in Protocol	a)	b)	c)	d)	e)
Baseline	Day 1	Last non-missin	ng value on or prio	or to day 1 (inclu	sive)	
Week 2	Day 15	2 to 22				
Week 4	Day 29	23 to 43	2 to 43	2 to 57		
Week 8	Day 57	44 to 71	44 to 71			
Week 12	Day 85	72 to 99	72 to 99	58 to 127	2 to 127	
Week 16	Day 113	100 to 127	100 to 127			
Week 20	Day 141	128 to 155	128 to 155			
Week 24	Day 169	156 to 183	156 to 183	128 to 267	128 to 267	
Week 28	Day 197	184 to 211	184 to 211			
Week 32	Day 225	212 to 239	212 to 239			
Week 36	Day 253	240 to 267	240 to 267			
Week 40	Day 281	268 to 295	268 to 295			
Week 44	Day 309	296 to 323	296 to 323			
Week 48	Day 337	324 to 351	324 to 351			
Week 52	Day 365	352 to 376	352 to 376	268 to 376	268 to 376	2 to 376
Follow-up	Day 386	Last treatment + 2 days and onwards				

a) Apply to Clinical laboratory and urinalysis

b) Apply to Vital signs

- c) Apply to Blood PD/PK sample, EQ-5D-5L, MENQoL
- d) Apply to C-SSRS
- e) Apply to 12-lead ECG

For TVU and DXA, the week 52 analysis window is day 2 to last treatment + 30 days. For endometrial biopsy, refer to Section 6.5.5 for analysis window.

As a general rule, if more than one observation exists within the analysis window, the observation closest to the scheduled visit day will be selected for that visit. If there are two observations that have the same distance from the scheduled day, the value that is after the scheduled day will be selected in the analysis. If more than one observation is made on the same day, an average value if continuous or the worst value if categorical will be included in the analysis.

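### A crisis-delayed Week 4 hormone or drug-level sample drawn on Days 58 to 60 is filed under Week 12, dropped if an on-time Week 12 sample exists, and leaves Week 4 blank

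*Protocol*

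**What the plan says.** **Sampling schedule.** Table 1 of the protocol (footnotes r and s) schedules hormone samples at Day 1 and Weeks 4, 12, 24, 52 and 55, and drug-level samples at Weeks 4, 12, 24 and 52. Neither is due at Week 8. Footnote c sets the ordinary visit tolerance: "Subjects will return to the study site for visits and procedures to occur within ± 3 days of the scheduled day".

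**Crisis rule.** Table 3 in protocol section 12.7 has the same entry for both sample types: "Delay the measurements to subsequent visit". Its columns run to Visits 15 and 16. No visit is exempted, and no rule says which visit the delayed sample should count for. Section 12.7 allows these measures only in a crisis and after discussion with the medical monitor.

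**Analysis windows.** SAP section 6.10.1 places these samples under column (c), whose footnote reads "Apply to Blood PD/PK sample, EQ-5D-5L, MENQoL". In that column Week 4 is Days 2-57, Week 12 is Days 58-127, Week 24 is Days 128-267 and Week 52 is Days 268-376. For competing values the rule is: "if more than one observation exists within the analysis window, the observation closest to the scheduled visit day will be selected for that visit". Ties go to the later value.

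**COVID-19 provisions.** SAP Appendix 1 lists additional analyses under sections 6.2.2, 6.3, 6.5.1 and 6.5.2.1. None deals with delayed hormone or drug-level samples.

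**The concern.** The protocol names a replacement for a missed Week 4 sample, and the SAP's window can file that replacement under a different visit. A site may follow Table 3 exactly, see the woman within the Visit 4 tolerance, and still supply a value that the by-visit summary discards. Changes in sex hormones and SHBG at Week 4 are listed exploratory endpoints in both documents, and protocol section 7.7 plans summaries of plasma concentration by visit. At stake is a lost Week 4 value or, less often, a Week 12 value that was really the Week 4 replacement.

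**Working it through.** **Inputs.** Scheduled days are 29 (Week 4), 57 (Week 8), 85 (Week 12), 113 (Week 16), 169 (Week 24), 197 (Week 28), 365 (Week 52) and 386 (Week 55), from protocol Table 1. The tolerance is ±3 days for the visits used below, apart from Week 52. Column (c) limits and the selection rule come from SAP section 6.10.1.

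**1. Reproduce the SAP's limits.** They are the midpoints between successive sampling days:
- (29 + 85)/2 = 57
- (85 + 169)/2 = 127
- (169 + 365)/2 = 267
- (365 + 386)/2 = 375.5, rounded to 376

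All four match. Column (c) was built on the sampling schedule without delayed samples.

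**2. Place a Week 4 sample delayed to Visit 4.** Visit 4 is in tolerance on Days 57 − 3 = 54 to 57 + 3 = 60. Days 54-57 (4 of 7) fall in Week 4. Days 58, 59 and 60 (3 of 7) fall in Week 12.

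**3. Apply the selection rule with an on-time Week 12 sample.** An on-time sample lies on Days 82-88, at most 3 days from Day 85. The replacement lies 85 − 58 = 27, 85 − 59 = 26 or 85 − 60 = 25 days away. It always loses, and nothing is left in the Week 4 window.

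**4. Apply the rule when Week 12 is also delayed, to Visit 6 (Days 110-116).** These samples lie 25 to 31 days from Day 85.

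| Week 4 replacement | Distance from Day 85 | Visit 6 days on which it is kept as Week 12 |
|---|---|---|
| Day 58 | 27 | 113-116 (4 of 7) |
| Day 59 | 26 | 112-116 (5 of 7) |
| Day 60 | 25 | 111-116 (6 of 7) |

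On the remaining days the Visit 6 sample is closer, or ties and wins as the later value. With Visit 6 on its scheduled Day 113 (28 days away), the Week 4 replacement is kept in all three rows and the true Week 12 replacement is dropped.

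**5. Check the other delays.** Week 12 delayed to Visit 6 (Days 110-116) stays inside 58-127. Week 24 delayed to Visit 9 (Days 194-200) stays inside 128-267. Neither is misfiled.

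**6. Check the proposed limit.** With Week 4 at Days 2-60 and Week 12 at Days 61-127, all 7 of 7 Visit 4 days map to Week 4. The earliest in-tolerance Week 12 visit is 85 − 3 = Day 82, so no scheduled sample collides.

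**7. Check Week 52.** The visit after Visit 15 is Visit 16, about 21 days after the last dose. Protocol section 1.3.2 gives a "terminal half-life ranging between 4-6 hours in healthy subjects and patients", so the sample is 21 × 24/6 = 84 to 21 × 24/4 = 126 half-lives after the last dose. SAP sections 6.5 and 6.10.1 close the on-treatment period one day after the last dose, so the sample is filed as Follow-up and Week 52 is missing.

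**The case against.** **The boundary is principled.** A sample on Days 58-60 is 29 to 31 days after the Week 4 target and 25 to 27 days before the Week 12 target, so it is nearer to Week 12. That explains the boundary. It does not justify discarding the sample that the protocol designates as the Week 4 replacement.

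**Several things must coincide.** There must be a crisis at Week 4, an in-person Visit 4, and that visit on Days 58-60 rather than Days 54-57. For the value to be dropped, a closer Week 12 sample must also exist. This stands: 3 of 7 is a count of calendar days, not a probability. Footnote c also allows unscheduled visits, so taking the subsequent visit to mean the next scheduled one is an assumption, though the natural reading of Table 3.

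**The data are not erased.** Protocol section 5.7.3 has exact drug-level sampling and last-dose times recorded, section 7.8 lists hormone values with sampling times, and SAP section 6.2.2 flags COVID-19 impact in listings. The SAP itself only lists plasma concentrations. This limits the harm to by-visit summaries but does not restore the Week 4 value there.

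**Moving column (c) would reach further.** EQ-5D-5L and MENQoL share that column, and Table 3 does not delay them to a later visit. This stands, and any change must be confined to the blood samples.

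**The stronger reading, on Week 52.** A reader might infer that the delay rule loses the final on-drug value, or lets an off-drug value pass as Week 52. The documents do not support either. The SAP already files such a sample as Follow-up, so nothing is contaminated. If the sample cannot be taken at Visit 15, Week 52 is missing with or without the delay rule. A Week 55 hormone sample is scheduled anyway, so for hormones the rule neither adds nor removes anything. For drug levels it directs only a needless draw.

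**Conclusion.** The Week 4 point holds and is minor. On 3 of the 7 permitted Visit 4 days, a replacement taken as Table 3 directs is assigned to Week 12. With an on-time Week 12 sample it is dropped and Week 4 is blank. With Week 12 also delayed to about Day 113, it can be reported as Week 12. Nothing in protocol section 12.7 or the SAP's COVID-19 provisions repairs this.

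The effect is limited to exploratory by-visit hormone summaries and the by-visit concentration summaries of protocol section 7.7. The primary safety and endometrial analyses are untouched. The documents do not give the number of women affected. It is probably small, since only crisis-delayed Week 4 samples are exposed. The conclusion assumes that the subsequent visit is the next scheduled one and that Visit 4 keeps its ±3 days.

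For Week 52 there is only a mismatch of wording. Table 3 does not exempt Visit 15, while the synopsis, section 2.2.1 and Table 1 footnote y require that visit in clinic.

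**What to change.** In SAP section 6.10.1, separate hormone and drug-level samples from EQ-5D-5L and MENQoL, and for the blood samples adopt one of two rules:

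- Analyse a crisis-delayed sample under the visit it replaces. This needs the delay to be identifiable in the database. Section 12.7 already has sites document each alternate measure and its time point in the source record.
- Set Week 4 to Days 2-60 and Week 12 to Days 61-127. This needs no new data. It would, however, also move an early-discontinuation sample drawn on Days 58-60 from Week 12 to Week 4, which the first rule avoids.

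Under either rule some Week 4 values would be up to 60 − 29 = 31 days late, so flag them in the summary or show it with and without them.

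Separately, reconcile Table 3 with the passages requiring Visit 15 in clinic, and state how a missed Week 52 sample is recorded. This removes a pointless off-drug draw but recovers no Week 52 value.

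The cost is one extra column or one sentence in the SAP, and one line in Table 3. No sampling is added.
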